For this means, we have designed a randomized controlled study with careful controls. Our study population is comprised of 240 BC patients in palliative and curative care (comprised of 50% Jewish and 50% Arab). This population will be randomized (using a permuted block design to account for ethnicity and level of traditionalism) to receive a standard art therapy intervention or a comparison group. The intervention is designed to increase emotion processing via art making in a supportive environment. The sham Art Therapy comparison group will engage in the coloring of prefabricated shapes (mandalas) and will receive Psychoeducation on topics related to coping with BC, identical to the topics of the AT group. This design will allow the study to test the mechanism of AT that is beyond the effects of time with a group, focus on a task and engagement with art materials.

Interventions and Duration

The AT intervention is an 8-week group intervention comprised of 8 1.5-hour weekly sessions conducted by an experienced Art Therapist who received special training in conducting the treatment protocol as designed. The intervention and comparison group were piloted on BC patients at Beilinson hospital and the protocol was modified based on feedback from the participants. Each intervention module is described below.

The comparison group will be an 8-week group intervention comprised of 8 1-hour weekly mandala coloring sessions with a self-care educational component, conducted by someone with experience conducting groups who will be trained in providing a well-planned comparison group, with fidelity checks that includes coloring pre-fabricated mandalas.

There will be an additional follow up time point 8 weeks after the intervention is over to assess

the lasting effects of the intervention.

Sample Size and Population

240 BC survivors will be randomized to the intervention and comparison groups. We are targeting 300 women and expect an attrition rate of 15%. We also will be targeting the recruit of 50% of our sample to be of Arab origin and 50% Jewish.

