4.1 Inclusion Criteria

1) adult (>18) females with initial or recurrent BC; 2) study entry within one year of diagnosis and 3 months after adjuvant cancer care (chemotherapy and radiotherapy (RT)) or reconstructive surgery; any additional or replacement standard medical treatment for cancer is allowed (i.e., surgery, chemotherapy, radiotherapy, neo-adjuvant chemotherapy, endocrine therapy); 4) additional medication is allowed, excluding what is described in exclusion criteria, and will be assessed for potential inclusion as a covariate; 5) can complete assessments in Arabic or Hebrew; 6) provides informed consent.

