8.2 Sample Size and Randomization

A power analysis was conducted via Monte Carlo simulation in Mplus showed that a sample size of 240 (120 per condition), provides: (1) >90% power to detect a moderate effect size (Cohen's $d = 0.50$) of treatment on mechanisms, (2) >90% power to detect a moderate association ($r = 0.30$) between mechanisms and symptoms, and (3) >90% power to detect an indirect effect from treatment to symptoms via mechanisms. The sample size will also provide >80% power to detect a moderate effect size for the Condition by Ethno-Cultural group interaction.

Consented participants will be randomized into the Art Therapy or Sham condition using block randomization stratified by site, ethnicity and traditionalism to ensure equal sample sizes between groups over time in each site and in each ethnicity. Permutations of group assignment will be generated in random blocks of 4, 6, and 8 so that staff cannot guess the condition of the final participant as the block size varies. Condition assignment will be stored in sealed, numbered envelopes to be opened consecutively as subjects enroll and the envelopes will designate individuals to the intervention through use of a random numbers table. PI [name] will provide the PhD students with the randomized lists (60 each cohort), who will schedule sessions and make weekly calls to encourage attendance, therefore both will be un-blinded to study assignment. The Research Nurse will collect and enter data, collect bio specimens and manage the database, and thus will be un-blinded after randomization. The research assistant (RA) will remain blinded throughout the study, and will receive lists of participants to call, without knowing which group they are assigned to. Participants will be told they are participating in an "art making" study where they will be assigned to an art making group. Participants will not be told which is expected to be superior.

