8.3 Treatment Assignment Procedures

Consented participants for each cohort will be randomized (PI- [name]) The University statistician will generate numbered envelopes to be opened consecutively as subjects enroll and the envelopes will designate individuals to the intervention through use of a random numbers table. PI [name] will provide the PhD students with the randomized lists (60 each cohort), who will schedule sessions and make weekly calls to encourage attendance and conduct the intervention and thus will be unblinded. The Research Nurse will collect and enter data, collect bio specimens and manage the database, but will remain blinded after randomization. The research assistant will remain blinded throughout the study, and will receive lists of participants

to call, without knowing which group they are assigned to. Participants will be told they are participating in an “art making” study where they will be assigned to either the intervention group or the sham intervention (Mandala) group. Participants will not be told which is expected to be superior.

Table 4: Roles in the study

Title	Blinded to group assignment	Roles	Rambam	Ziv	Beilinson
Research nurse (employee of each hospital).	Yes	Recruit and obtain verbal consent, collect blood.	1	1	1
Research coordinator (employee of each hospital).	Yes	Assist MD in recruiting patients, collect data (questionnaires and HRV), transfer blood to the lab for processing (separation to serum, divide in 4 aliquots and cryopreservation -80)	1	1	1
Art Therapist	No	Conduct intervention groups (8.5 weeks)- Art Therapy and SHAM in Hebrew or Arabic	2	2	2
PhD student	No	Conduct groups, supervise interventionists, assist in fidelity assurance, assist in data analysis.	3		
Laboratory worker	Yes	Conduct inflammatory cytokines analysis.	1		
Research coordinator	Yes	Coordinate between study site, transport frozen serum to lab, input data	1		

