9.3 Quality Assurance

9.3.1 Training

Interventionists will be experienced MA level art therapists who will be trained by PI [name] and the PhD students. Weekly and bi-weekly training session will be conducted prior to commence of the proposed research, and PI [name] will be available for additional support and guidance as needed.

To ensure the quality and consistency of the intervention the interventionists of both the intervention and comparison groups will be scored each session (see Table 2) and against the treatment manual reviewed by the blinded RA. Discrepancies will be flagged and then reviewed by PI [name], who will subsequently address this with the intervention team for correction. Adherence to the study regimen will be defined as attending 80% of the group sessions, which will be monitored and recorded by the interventionist.

Each of the three hospitals that have approved their participation in this study have an independent Institutional Review Board (IRB), which approve the conduct of clinical trials. The boards strictly adhere to the Helsinki Treaty on Human Medical Experimentation. Hospitals consent to the Public Health Regulations (Medical Experiments in Human Subject) – 1980 of Israel Ministry of Health, including additions and amendments, and operate in accordance with the regulations for conducting Medical Trials on Humans – 1999 of the Pharmacological Unit of the Israel Ministry of Health provisions of the current Harmonized International Guidelines for Good Clinical Practice namely: ICH-GCP.

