9.3.3 Monitoring

PI [name] will closely monitor and supervise the research team at their respective sites, as well as conduct coordinated oversight of psychological status of all participating women taking part in the research. She will consult with PI [name] with any concern or consideration. PI [name] will also meet regularly with the research teams at the clinical sites and the University every other week to ensure appropriate conduct.

All local legal requirements regarding protection of personal data must be adhered to.

To ensure the quality and consistency of the intervention administration both the intervention and comparison groups in both Hebrew and Arabic will be scored against the treatment manual, using a check list which will be assessed daily by the research assistant who is blind to group allocation. Adherence to the study regimen will be defined as attending 80% of the group sessions, which will be monitored and recorded by the interventionist. Participant confidentiality will be well protected, as any data, specimens, forms, reports, and other records that leave the site will be identified only by a participant identification number (PID). All records will be kept in a locked file cabinet. All computer entry and networking programs will be done using Patient ID numbers only. Information will not be released without written permission of the participant, except as necessary for monitoring by IRB.

The Board will issue a report every six months to the PI and annually to the IRB.

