Hypothesis 3: the effect of AT versus SHAM on emotional processing will be stronger in women from an ethno-cultural minority group will be tested by expanding the linear mixed models from Hypothesis 1 by including measures of traditional values as a covariate and a Time x Condition x Ethno-Cultural Group (Jewish vs Arab) interaction to test whether ethno-cultural group moderates the Time x Condition interaction from Hypothesis 1. If the three-way interaction is significant, simple slopes will be calculated and graphed to characterize the change in emotion processing by treatment condition and ethno-cultural group.

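### Table 4 suggests few group leaders per language, and Hypothesis 3 has no leader, group or language term, so a leader difference in the AT-versus-Mandala effect could be read as ethno-cultural moderation

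*Protocol*

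**What the plan says.** **Who leads.** Table 4 in Protocol section 8.3 gives two art therapists at each of the three sites, six in all, with the role "Conduct intervention groups (8.5 weeks)- Art Therapy and SHAM in Hebrew or Arabic". The same table lists three PhD students whose role reads "Conduct groups, supervise interventionists, assist in fidelity assurance, assist in data analysis"; their language and arm are not given. Section 9.3.1 says "Interventionists will be experienced MA level art therapists who will be trained by PI". The Interventions and Duration paragraph of the protocol summary describes the comparison group differently, as "conducted by someone with experience conducting groups who will be trained in providing a well-planned comparison group", which need not be an art therapist or the person who leads the AT groups.

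**Which language.** Section 9.3.3 confirms that both arms run in both languages: "both the intervention and comparison groups in both Hebrew and Arabic will be scored against the treatment manual". The only language condition on participants, in section 4.1, is "can complete assessments in Arabic or Hebrew". It is not tied to ethnicity.

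**Which test.** SAP C.5.2, Hypothesis 3, extends the Hypothesis 1 mixed model with traditional values as a covariate and a three-way "interaction to test whether ethno-cultural group moderates the Time x Condition interaction from Hypothesis 1". No leader, therapy-group or language term is named under Hypothesis 1 or Hypothesis 3. Randomization (section 8.2) is stratified by site, ethnicity and traditionalism.

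**The concern.** The AT sessions end with 30 minutes of group discussion (sections 3 and 5.2), so the language of a group is likely to restrict who can lead it and who can attend. If Hebrew groups are mostly Jewish women with one set of leaders, and Arabic groups are mostly Arab women with another, the Hypothesis 3 contrast compares two small sets of leaders as well as two populations. A leader who gets more out of AT relative to Mandala than a colleague does would then contribute to the apparent ethnic difference. The planned model tests that difference against variation between women only. The traditional-values covariate does not address this.

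At stake is the second study objective in Protocol section 1, the ethno-cultural difference in the effect of AT. This differs from ordinary correlation within therapy groups, because one leader may run several groups and a group term alone does not capture what those groups share.

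**Working it through.** **The plan's own figure.** Section 8.2 and SAP C.5.1 state more than 80% power for a moderate Condition by Ethno-Cultural interaction with a "sample size of 240 (120 per condition"). Moderate is not defined for this term. I assume two-sided 5%. With equal ethnic halves (section 4) there are 240/4 = 60 women per cell, and on an outcome with SD 1 the contrast has SE = sqrt(4/60) = 0.258.

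- Difference of 0.5 SD between the two ethnic groups' effects, unadjusted: Phi(0.5/0.258 - 1.96) = 49.1%.
- The same with baseline adjustment, variance 1 - r^2: 77.4% at r = 0.70 and 83.3% at r = 0.75.
- Cohen f = 0.25: 97.1%.

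The stated figure can be neither confirmed nor called wrong. Nothing in the documents says that it allows for leaders.

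**Inputs for the check.** From the documents: 60 women per cell and six art therapists leading both arms (Table 4). Assumed: three leaders per ethnicity, each serving one ethnic group only; outcome SD 1; no true moderation; leader-specific AT-minus-Mandala effects varying with SD tau.

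**What cancels.** If the same person leads both arms, her general effect on outcomes enters both and drops out of AT minus Mandala. Only tau remains:

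Var(contrast) = 4/60 + 2 x tau^2/3

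False-positive rate = 2 x Phi(-1.96 x SE_planned/SE_true), with SE_planned = 0.258.

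| tau | SE_true | SD of spurious difference, sqrt(2 tau^2/3) | False-positive rate |
|---|---|---|---|
| 0 | 0.258 | 0 | 5.0% |
| 0.1 | 0.271 | 0.08 | 6.2% |
| 0.2 | 0.306 | 0.16 | 9.8% |
| 0.3 | 0.356 | 0.24 | 15.5% |

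A simulation of 20,000 runs agrees. With a general leader SD of 0.3 and tau = 0 the rate is 4.5%; with tau = 0.3 and no general leader effect it is 15.1%.

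**Variations.**

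- *Smaller residual variance.* At 0.51 (baseline correlation 0.7, 1 - 0.7^2) the rates at tau 0.1, 0.2 and 0.3 are 7.3%, 14.2% and 23.8%.
- *More leaders.* Replace 2 tau^2/3 by 2 tau^2/k. Counting the PhD students gives nine leaders, k = 4.5 per ethnicity. At tau 0.2, 4/60 + 0.08/4.5 = 0.0844, SE 0.291, rate 8.2%. With k = 6 it is 7.4%.
- *A therapy-group term alone.* Assume 4 cohorts x 3 sites x 2 arms x 2 languages = 48 groups, so 240/48 = 5 women each. A group-level test on 44 df (6,000 simulated runs, no group correlation) still rejects in 8.4% at tau 0.2 and 12.4% at tau 0.3.
- *Different leaders in the two arms.* General leader differences no longer cancel. With three leaders per cell and 20 women each, the design effect is 1 + 19 x ICC. ICC 0.02, 0.05 and 0.10 give 1.38, 1.95 and 2.90, and false-positive rates of 9.5%, 16.0% and 25.0%.

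**Power of a leader-level check.** A test on six leader-specific effects (4 df), for a true difference of 0.5 SD and residual variance 1, has 32% power at tau 0 and 24% at tau 0.2.

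**The case against.** The strongest reply is that the nesting is not in the text. A reader might infer from two therapists per site and the words on language that each site has one Hebrew and one Arabic therapist, so that Hypothesis 3 compares three therapists with three. The documents do not say this. They do not exclude bilingual leaders or Arab women in Hebrew groups, two per site may simply reflect workload, and the PhD students enlarge the pool. Any such overlap makes the confounding partial. This stands, and it is why the point is conditional.

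A reader might also infer that any difference in skill between the two sets of therapists would bias Hypothesis 3. If Table 4 holds and the same people lead both arms, it would not; only a leader-by-Condition difference matters. The protection is lost if the comparison arm has other leaders, as the protocol summary allows.

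Finally, tau is undocumented, and the protocol works to keep it small: described sessions (section 5.2), observational checks on 20% of sessions with retraining when average fidelity falls below 4 (section 5.4), and common training with scoring of each session (section 9.3.1). At tau 0.1 the inflation is slight. But fidelity scoring can only narrow leader differences; it cannot separate what remains from ethnicity, and the plan does not say that the leader of each group enters the analysis data.

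**Conclusion.** The point holds as a conditional one. The plan does not say how leaders and languages map to ethnicity and arm, and the Hypothesis 3 model has no term that would separate them. To the extent that leaders serve one ethnic group only, the planned test rejects too often: about 6%, 10% and 16% at tau 0.1, 0.2 and 0.3 with three leaders per ethnicity, and about 8% at tau 0.2 with nine leaders in all. With different leaders in the two arms it can be worse, at 16% for a leader ICC of 0.05. Tau, the ICC, the number of leaders per ethnicity and the two-sided 5% level are assumptions.

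The documents do not support the conclusion that therapist is fully nested in ethnicity, or that a positive Hypothesis 3 result would be uninterpretable whatever the allocation. The point concerns the moderation claim only. It is worth acting on because the change is cheap and bears on what the trial can conclude about its second objective.

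**What to change.** 1. Reconcile the protocol summary with Table 4 on who leads the comparison arm, and state the allocation of leaders, PhD students included, by language and arm.
2. Record leader, group and language of delivery for every participant.
3. Add to SAP Hypothesis 3 a sensitivity analysis with random effects for leader, leader-by-Condition and therapy group, using small-sample degrees of freedom. Report the leader-specific AT-minus-Mandala effects by language, descriptively.
4. If leaders prove to be nested in ethnicity, report the result as a difference that cannot be separated from language of delivery and leader.

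I would not make the moderation claim depend on leader-specific effects agreeing within each language. With 20 women per arm per leader, each effect has SE sqrt(2/20) = 0.32, and three identical leaders would show an expected range of about 1.69 x 0.316 = 0.53 SD by chance. Such a rule would block true results on noise.

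The cost is three recorded variables and a few sentences in the SAP. The downside is a more modest Hypothesis 3 claim and a low-power sensitivity analysis, which qualifies the main test and does not replace it. A random effect gives a more honest standard error but does not remove complete confounding, so step 4 is needed as well.

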9. DATA COLLECTION AND QUALITY ASSURANCE

9.1 Data Collection Forms

PI [name] will provide the research coordinators with the randomized lists (60 each cohort), who will schedule sessions and make weekly calls to encourage attendance, therefore both will be un-blinded to study assignment. The Research Nurse will collect and enter data, collect bio specimens and manage the database, and thus will be un-blinded after randomization. The research assistant will remain blinded throughout the study, and will receive lists of participants to call, without knowing which group they are assigned to. Signed

consent forms and all study questionnaires will be kept in an administrative office separate from research data and available for audit even when the PI is not. Additional information contained in this case book will be relevant demographic and medical/psychiatric information about the subject obtained during the interview with the site representative. Because this case book will contain personal identifiers and PHI, it will be kept separate from any data gathered as part of the study and will be kept in a locked office.

9.2 Data Management

At the point of first contact by potential participant contacting us, a brief overview of the study will be provided by the study coordinator. At screening, the consent form will be reviewed, and potential subjects will have an opportunity to address any concerns they might have. During this conversation, the detailed nature, purpose, procedures, benefits, risks of, and alternatives to this study will be explained to each subject and written informed consent will be obtained by the site PI. Informed consent will be documented on a Hospital IRB-approved form. A copy of the signed form will be given to the subject. Signed consent forms will be kept in a locked office in the hospital, which is an administrative office separate from research data and available for audit even when the PI is not. Additional information contained in this case book will be relevant demographic and medical/psychiatric information about the subject obtained during the interview with the site representative. Because this case book will contain personal identifiers and PHI, it will be kept separate from any data gathered as part of the study and will be kept in a locked office. After consent is obtained, potential subjects will be screened by study personnel to determine that the subject meets all inclusion and exclusion criteria for study participation. The contact MD at each site will be contacted immediately in the event of a subject meeting criteria for major depression or any other acute untreated psychiatric condition or for suicidal ideation. All such subjects will be evaluated for the need for acute hospitalization for safety and will be given appropriate treatment referrals.

9.3 Quality Assurance

9.3.1 Training

Interventionists will be experienced MA level art therapists who will be trained by PI [name] and the PhD students. Weekly and bi-weekly training session will be conducted prior to commence of the proposed research, and PI [name] will be available for additional support and guidance as needed.

To ensure the quality and consistency of the intervention the interventionists of both the intervention and comparison groups will be scored each session (see Table 2) and against the treatment manual reviewed by the blinded RA. Discrepancies will be flagged and then reviewed by PI [name], who will subsequently address this with the intervention team for correction. Adherence to the study regimen will be defined as attending 80% of the group sessions, which will be monitored and recorded by the interventionist.

Each of the three hospitals that have approved their participation in this study have an independent Institutional Review Board (IRB), which approve the conduct of clinical trials. The boards strictly adhere to the Helsinki Treaty on Human Medical Experimentation. Hospitals consent to the Public Health Regulations (Medical Experiments in Human Subject) – 1980 of Israel Ministry of Health, including additions and amendments, and operate in accordance with the regulations for conducting Medical Trials on Humans – 1999 of the Pharmacological Unit of the Israel Ministry of Health provisions of the current Harmonized International Guidelines for Good Clinical Practice namely: ICH-GCP.

